### **8.3.3 Packaging and Labeling**

Packaging: Each nasal spray is supplied in glass bottles with nasal spray pump applicator and cap. If the shipment arrives in larger bottles (not packaged for individual-use), Abbotts Pharmacy or designated study staff will repackage the nasal sprays into 40 IU/1 ml doses in glass bottles with nasal spray pump applicators and caps.

Labeling: Wellspring Compounding Pharmacy or designated staff will remove any labels that the vendors have placed.

## **8.4 Supply of Study Drug at the Site**

One of the three pharmacies/manufacturers described above will ship the oxytocin and placebo bottles to the investigational site, San Francisco VA Medical Center. The initial study oxytocin and placebo shipment will be shipped after site activation (i.e., all required regulatory documentation has been received by the Principal Investigator and a contract has been executed). Subsequent study drug shipments will be made after initial supply of oxytocin and placebo has run low. Care will be taken to ensure that the study drug supplier is never changed during the course of an active study. However, unpredictability in obtaining the study drug in a timely

fashion from the original manufacturer has led us to institute alternative manufacturing options.

#### **8.4.1 Dosage/Dosage Regimen**

Oxytocin and placebo (saline) solution will be administered intranasally followed by a resting period in a neutral environment. The oxytocin dose is comparable to that used previously in human studies of behavior (Davies et. al. 2019). In the first phase of the study, subjects will receive one administration of either oxytocin or placebo on two separate sessions at least one week apart. No adjustments for weight, age, and meals will be made. In the second phase, subjects will self-administer oxytocin or placebo twice daily for three weeks (18-24 days). Again, no adjustments for weight, age, and meals will be made.

#### **8.4.2 Dispensing**

The investigator has the authority to dispense the drug. Trained study staff will be instructing participants to administer the nasal spray from a safe distance to limit close contact.

#### **8.4.3 Administration Instructions**

It is preferable to sit when using the nasal spray.

During the acute phase, study staff will administer the nasal spray to participants with these instructions:

Remove the flip-off cap. Holding the bottle upright, insert the nozzle into one nostril and actuate while the participant gently inhales through nose and exhales through mouth. Switch nostrils and repeat. Keep switching nostrils, actuating, inhaling, and exhaling until all the oxytocin or placebo solution has been used up.

During the chronic phase, subjects will administer the nasal spray themselves with these instructions:

Remove the flip-off cap. Holding the bottle upright, insert the nozzle into one nostril and actuate while gently inhaling through nose and exhaling through mouth. Switch nostrils and repeat. Keep switching nostrils, actuating, inhaling, and exhaling until all the oxytocin or placebo solution has been used up.

#### **8.4.4 Storage**

Study drug should be stored at the study site in a refrigerator (2-8oC). If the temperature of the study drug storage exceeds or falls below this range, this should be reported to the Principal Investigator and captured as a deviation. Subjects will be instructed to store the medication in provided packaging and in a refrigerator.

### **8.5 Study Drug Accountability**

---

An accurate and current accounting of the dispensing and return of study drug for each subject will be maintained on an ongoing basis by a member of the study site staff. The number of study drug dispensed and returned by the subject will be recorded on the Investigational Drug Accountability Record. The study monitor will verify these documents throughout the course of the study.

## **8.6 Measures of Treatment Compliance**

Adherence to and administration technique of administering the study drug will be directly observed for all groups via secure video calls between participants and study coordinators during Video Observed Therapy (VOT) procedure. Participants may use tablets provided by the VA or their own devices.

In order to safeguard the well-being of all subjects enrolled in the study, each subject will be monitored for the following:

- a. Adverse Event: Any untoward medical occurrence in a subject that does not necessarily have a causal relationship with the assessment procedures. Will include any unfavorable and unintended clinical sign, symptom, or illness temporally associated with the use of the assessment, whether or not considered related to it.
- b. Serious Adverse Event: Any adverse experience that results in any of the following outcomes: death, a life-threatening experience, acute psychiatric decompensation, inpatient hospitalization, or a persistent or significant disability/incapacity.
- c. Unexpected Adverse Event: Any adverse experience the specificity or severity of which is not consistent with the risks information described in this study protocol or consent/assent document

## **9 STUDY PROCEDURES AND GUIDELINES**

A Schedule of Events representing the required testing procedures to be performed for the duration of the study is diagrammed in Appendix 1.

Prior to conducting any study-related activities, written informed consent and the Health Insurance Portability and Accountability Act (HIPAA) authorization must be signed and dated by the subject.

### **9.1 Clinical Assessments**

#### **9.1.1 Concomitant Medications**

All concomitant medication and concurrent therapies will be documented at Baseline/Screening and at Study Days when applicable. Dose, route, unit frequency of administration, and indication for administration and dates of medication will be captured.

#### **9.1.2 Demographics**

Demographic information (date of birth, gender, race) will be recorded during the visit.

#### **9.1.3 Medical History**

Relevant medical history, including history of current disease, other pertinent respiratory history, and information regarding underlying diseases will be recorded during the visit.

#### **9.1.4 Vital Signs**

Blood pressure and pulse will be recorded during the visit.

#### **9.1.5 fMRI Testing**

Subjects will perform theory of mind tasks in the San Francisco Veterans Affairs Medical Center's on-site MRI research facility. Participants are asked to lie in the scanner with only their head placed in the fMRI and visual stimuli are presented on a screen. The task administrator is able to communicate through an intercom system. Task specific instructions are displayed on a computer screen and responses are collected through a button box.

---

### **9.1.6 Social Functioning Test**

Subjects will perform social functioning tasks in [name] Bonding and Attunement in Neuropsychiatric Disorders laboratory. Participants will be asked to complete several measures of social functioning, social ability, negative symptoms, and Theory of Mind.

### **9.1.7 Adverse Events**

Information regarding occurrence of adverse events will be captured throughout the study. Duration (start and stop dates and times), severity/grade, outcome, treatment and relation to study drug will be recorded on the case report form (CRF).

## **9.2 Clinical Laboratory Measurements**

### **9.2.1 Pregnancy Test**

For those who can become pregnant, a urine pregnancy test will be obtained during each in-person visit.

## **10 EVALUATIONS BY VISIT**

### **10.1 Visit 1 (Day 1, Remote Visit)**

1. Review the study with the subject (subject's legal representative) and obtain verbal informed consent and HIPAA authorization, if appropriate.
  1. During the covid-19 pandemic, Visit 1 tasks and procedures have been adapted to be remote. We will be collecting verbal consent by video call at the beginning of this visit. Written informed consent will be obtained during Visit 2, the first in-person visit, before study drug administration.
2. Assign the subject a unique screening number.
3. Record demographics data.
4. Record medical history, including a history of psychosis, diagnosis date, and prior antipsychotic treatments.
5. Record concomitant medications.

6. Structured Clinical Interview for DSM-5 (Diagnostic and Statistical Manual of Mental Disorders, 5th Edition)
7. Social functioning assessments.
8. Schedule subject for Visit 2 in one week from their first visit if visit hasn't been scheduled yet.

#### **10.2 Visit 2 (Week 1)**

1. Review the study with the subject (subject's legal representative) and obtain written informed consent and HIPAA authorization, if appropriate.
2. Urine Pregnancy Test
3. Oxytocin/placebo administration.
4. fMRI testing.

#### **10.3 Visit 3 (Week 2)**

1. Urine Pregnancy test
2. Oxytocin/placebo administration.
3. fMRI testing.

#### **10.4 Visit 4 (Week 3)**

1. Urine Pregnancy Test
2. Record changes to concomitant medications.
3. Record participant weight
4. ToM, negative and positive symptoms, and social ability assessments
5. Oxytocin/placebo administration
6. Oxytocin self-administration training.

#### **10.5 Chronic Period (Remote procedures between Visit 5 and Visit 6)**

1. VOT

2. Social Functioning assessment

## **10.6 Visit 5 (Week 6)**

1. Urine Pregnancy test
2. Record changes to concomitant medications.
3. Record participant weight
4. Perform and record vital signs.
5. Oxytocin/placebo administration.
6. ToM, negative and positive symptoms, and social ability assessments.

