#### **3.2 Secondary Objectives**

The secondary objective is to compare the acute effects of a single administration oxytocin vs. placebo, to the clinical and behavioral effects of chronic OT treatment vs. placebo in schizophrenia participants. The study will assess the effects of exogenous oxytocin on laboratory-based social interactions, Theory of Mind (ToM), and negative symptoms in participants with schizophrenia.

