### **4 STUDY DESIGN**

#### **4.1 Study Overview**

100 subjects are planned. During the fMRI phase, intranasal oxytocin and placebo will be administered to each subject in a randomized, double-blind, counterbalanced order with a cross-over design, at least one week apart. Testing will commence 45 minutes after drug administration and continue for no longer than 3 hours.

During the longitudinal phase, participants will then be randomized to receive approximately three weeks (18-24 day range) of twice daily administration of either OT or placebo. Testing will commence on baseline and after three weeks (18 to 24 days) of drug administration.

Screening data will be reviewed to determine subject eligibility. Subjects who meet all inclusion criteria and none of the exclusion criteria will be entered into the study.

The following treatment regimens will be used:

- Experimental treatment: Intranasal oxytocin
- Placebo: Saline solution

Total duration of subject participation will be 15 hours over 2 months.

---

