### **12.2 Demographic and Baseline Characteristics**

### **12.3 Analysis of Primary Endpoint**

The investigators will perform linear regression analyses with SFS change as the primary outcome and drug modeled as a 2-level dummy variable (drug vs. placebo). Identical analyses will be run using accuracy scores for the FBT and PDT instead of rTPJ activity to determine if acute OT improves ToM ability versus placebo.

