### **12.4 Analysis of Secondary Endpoints**

Similar analyses as stated in 15.3 will be conducted for the secondary clinical outcomes including social ability, negative symptoms (CAINS), and ToM(Hinting Task).

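### As listed, the assessment battery precedes study drug at Visit 4 but follows a fresh dose at Visit 5, so the chronic change, in ToM above all, cannot be separated from any acute effect of that dose

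*Combined protocol and SAP*

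**What the plan says.** Section 4.1 places longitudinal testing at the two ends of the treatment period: "Testing will commence on baseline and after three weeks (18 to 24 days) of drug administration". It gives no interval from the dose taken on the day of testing. The one interval it does give, "Testing will commence 45 minutes after drug administration and continue for no longer than 3 hours", belongs to the fMRI phase.

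The visit lists in section 10 supply the only order:
- Visit 4 (10.4): item 4 is the battery and item 5 is "Oxytocin/placebo administration".
- Visit 5 (10.6): item 5 is study drug administration and item 6 is the battery, "ToM, negative and positive symptoms, and social ability assessments".

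Between these visits, section 8.4.1 says that "subjects will self-administer oxytocin or placebo twice daily for three weeks (18-24 days".

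The secondary objective (3.2) is to "compare the acute effects of a single administration oxytocin vs. placebo, to the clinical and behavioral effects of chronic OT treatment vs. placebo". Section 12.4 applies the same type of regression as for the primary endpoint to "secondary clinical outcomes including social ability, negative symptoms (CAINS), and ToM(Hinting Task"). Section 12.3 also plans an analysis of task accuracy in the acute phase "to determine if acute OT improves ToM ability versus placebo".

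**The concern.** Visits 4 and 5 are the baseline and end points of the chronic comparison. If the lists are worked through in order, the baseline score is taken before that visit's dose and the end score after a new clinic dose. Only the oxytocin arm receives active drug at that moment. The change from Visit 4 to Visit 5 would then mix what three weeks of treatment did with what a single dose did on the day.

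This matters because section 3.2 sets acute effects against chronic effects. If the chronic measure may itself include an acute response, the comparison is hard to interpret, and an acute effect alone could be reported as a benefit of three weeks' treatment.

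**Working it through.** **1. The two visits side by side**

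| | Visit 4 (10.4) | Visit 5 (10.6) |
|---|---|---|
| Battery | item 4 | item 6 |
| Study drug | item 5 | item 5 |
| Battery relative to that visit's dose, as listed | before | after |

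Appendix 1 marks study drug and social functioning tests at both visits but gives no order within a visit. Nothing in the protocol holds the Visit 5 dose until after testing or sets an interval from it. Sections 12.3 and 12.4 do not separate an acute component from the chronic change.

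**2. Does list order mean time order?** Section 10 does not say so. Where other text fixes the sequence, the list agrees with it. At Visit 2 the list runs written consent, drug, fMRI. The synopsis requires written consent before drug, and section 4.1 starts fMRI-phase testing 45 minutes after the dose. Reading the lists as chronological is therefore reasonable, but it remains an inference.

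**3. What the contrast estimates.** Take effects as additive, oxytocin minus placebo:
- C = effect of three weeks' treatment that does not depend on a recent dose
- H = any remaining effect of a recent home spray
- A = acute effect of the Visit 5 clinic dose

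Visit 4, battery before the dose: expected difference between arms is 0 under randomisation. 
Visit 5, battery after the dose: C + H + A. 
Difference in change: (C + H + A) − 0 = C + H + A. 
With the Visit 5 battery before the clinic dose it would be C + H.

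Both arms take a spray, so expectancy cancels between arms. A pharmacological A does not.

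**4. Illustration of size.** The plan has no figure to reproduce here. Inputs:
- Arm sizes 55 and 40 (section 8.1), and 50/50 as an equal split of the planned 100.
- Two-sided alpha 0.05 (section 12.6).
- Assumed: C = 0, H = 0, and A = d in SDs of the change score. The documents give no value for d.

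Normal approximation: P(reject) = 1 − Φ(1.96 − d/se) + Φ(−1.96 − d/se), with se = √(1/n₁ + 1/n₂). 
55/40: se = √(1/55 + 1/40) = 0.208. 
50/50: se = √(1/50 + 1/50) = 0.200. 
For example, d = 0.2 at 50/50 gives d/se = 1.0, so P = 1 − Φ(0.96) + Φ(−2.96) = 0.170.

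| Assumed d | 55/40 | 50/50 |
|---|---|---|
| 0 | 5.0% | 5.0% |
| 0.1 | 7.7% | 7.9% |
| 0.2 | 16.1% | 17.0% |
| 0.3 | 30.3% | 32.3% |
| 0.4 | 48.6% | 51.6% |
| 0.5 | 67.2% | 70.5% |

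A t-test calculation for d = 0.1, 0.2 and 0.3 agrees to within about half a percentage point (7.6%, 15.9%, 29.8% at 55/40).

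**5. Units.** These figures hold for SDs of the change score. An effect of 0.2 raw-score SD equals 0.2/√(2(1 − r)) change-score SD, where r is the correlation between the two visits. At 50/50, r = 0.3 gives 0.169 and about 13%; r = 0.7 gives 0.258 and about 25%. Both values of r are assumed.

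**The case against.** The strongest reply is that the order is read from lists that are not declared chronological and are loosely drafted. Section 10.5 places the chronic period between Visits 5 and 6 although there is no Visit 6. Appendix 1 puts vital signs at Visit 4, while section 10 lists them at Visit 5. This stands as a limit on the inference. It does not remove the gap: if the order was not intended, timing is simply unspecified and could vary between participants or between the two sites named in the synopsis.

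Second, a baseline belongs before the first chronic dose, and an end assessment during continuing treatment is a legitimate on-treatment contrast. The plan never defines the chronic effect as a pre-dose effect. This also stands, and it is why labelling the result as on-dose is an acceptable remedy. The rejections in the table would then reflect a real drug effect attributed to the wrong cause, not a spurious difference between arms.

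Third, twice-daily home dosing means that a recent spray may act at Visit 5 even if the clinic dose comes later. A reader might infer that moving the battery ahead of the clinic dose settles the matter. It removes A but not H.

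A reader might also infer more than the documents support:
- **That the chronic change does contain an acute effect.** Section 12.3 treats the acute effect as a question to be tested. The supportable statement is that the two cannot be separated in this contrast. The crossover does estimate an acute ToM effect, but from FBT and PDT accuracy, not the Hinting Task.
- **That the Visit 5 battery falls 45 minutes to 3 hours after dosing.** That window is stated for the fMRI phase only.
- **That all three secondary outcomes are equally exposed.** The rationale in section 2 supports an oxytocin effect on ToM, but its negative-symptom evidence comes from three weeks of treatment. Section 5.2 assesses social skills remotely during the chronic period, so exposure of social ability depends on which measure is meant.
- **That the primary SFS result is affected.** The documents do not say that the SFS is taken in this block.

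**Conclusion.** The point holds as a mismatch between sections 10.4 and 10.6 together with missing timing rules. If the lists are followed in order, the Visit 4 to Visit 5 drug-placebo difference cannot be separated from any acute effect of the Visit 5 dose, and the comparison in section 3.2 loses its clear meaning. The concern is well supported for the Hinting Task, speculative for CAINS and uncertain for social ability.

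The size is unknown. At assumed acute effects of 0.1 to 0.3 SD of the change score and no chronic effect, the chance of a significant chronic result would be about 8% to 30% at 55/40 (8% to 32% at 50/50) against a nominal 5%. These figures rest on the listed order being followed, an acute effect that is only hypothesised, and no remaining home-dose effect.

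**What to change.** Reconcile sections 10.4 and 10.6 so that the battery's position relative to that visit's administration is stated and is the same at both visits. Alternatively, keep the listed order and label the Visit 5 result explicitly as an on-dose effect, chronic plus acute, in the objectives and in section 12.4.

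Under either choice, record the time since the last dose, clinic or home, at each battery and report it by arm. This is needed because home dosing may leave a recent-dose effect even when the battery precedes the clinic dose. Also state which measure social ability refers to and where it is taken.

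The cost is a wording change and one recorded time at each battery. The downside is that participants already assessed under the listed order need a flag in the dataset. An interval that was not recorded at the time may not be recoverable later. No dose or dosing rule is proposed here.

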## **10.7 Early Withdrawal Visit**

1. Record any Adverse Experiences and/or Review subject diary for adverse experiences and exclusionary medication use.
2. If given, collect and return unused oxytocin to pharmacy.

# **11 DISCONTINUATION AND REPLACEMENT OF SUBJECTS**

## **11.1 Early Discontinuation of Study Drug**

A subject may be discontinued from study treatment at any time if the subject, the investigator, or the Sponsor feels that it is not in the subject's best interest to continue. The following is a list of possible reasons for study treatment discontinuation: *(The list should match the Study Completion/Discontinuation CRF page.)*

- Subject withdrawal of consent (or assent)
- Subject is not compliant with study procedures
- Adverse event that in the opinion of the investigator would be in the best interest of the subject to discontinue study treatment
- Protocol violation requiring discontinuation of study treatment

- Lost to follow-up
- Sponsor request for early termination of study
- Positive pregnancy test (females)

If a subject is withdrawn from treatment due to an adverse event, the subject will be followed and treated by the Investigator until the abnormal parameter or symptom has resolved or stabilized.

All subjects who discontinue study treatment should come in for an early discontinuation visit as soon as possible and then should be encouraged to complete all remaining scheduled visits and procedures.

All subjects are free to withdraw from participation at any time, for any reason, specified or unspecified, and without prejudice.

Reasonable attempts will be made by the investigator to provide a reason for subject withdrawals. The reason for the subject's withdrawal from the study will be specified in the subject's source documents. Refer to Section 10 for early termination procedures.

### **12.3 Withdrawal of Subjects from the Study**

A subject may be withdrawn from the study at any time if the subject, the investigator, or the [name] feels that it is not in the subject's best interest to continue.

All subjects are free to withdraw from participation at any time, for any reason, specified or unspecified, and without prejudice.

Reasonable attempts will be made by the investigator to provide a reason for subject withdrawals. The reason for the subject's withdrawal from the study will be specified in the subject's source documents. As noted above, subjects who discontinue study treatment early (i.e., they withdraw prior to Visit X) should have an early discontinuation visit. Refer to Section 10 for early termination procedures. Subjects who withdraw after Visit X but prior to Visit X should be encouraged to come in for a final visit (and the procedures to be followed would include those for their next scheduled visit).

### **12.4 Replacement of Subjects**

Subjects who withdraw from the study treatment will be replaced.

Subjects who withdraw from the study will be replaced.

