STUDY DESIGN	This is a double-blind, placebo-controlled, counterbalanced order with a cross-over design one week apart, followed by a randomized,

	double-blind, three week (18-24 days) study design. We will also be implementing a response adaptive randomization (RAR) design after the first 60 participants complete the study. This will change the allocation ratio to favor the drug treatment arm with greater improvement in social functioning, while keeping adequate statistical power in all arms.
PRIMARY OBJECTIVE	The objective is to clarify how and in whom exogenous oxytocin improves social functioning in schizophrenia as measured by acute neural response patterns during social cognitive tasks and social functioning as measured by the Social Functioning Scale (SFS).
SECONDARY OBJECTIVES	
Social skills will be assessed during the chronic period over the phone or video chat. Participants will answer questions about their social interactions and experiences.
 
Theory of Mind (ToM) will be assessed using the Hinting Task a well validated audiovisual tool that incorporates social interferences.
 
Negative symptoms will be assessed with Clinical Assessment Interview for Negative Symptoms (CAINS), comprising two subscales reflecting the negative symptom factors. Data will be analyzed with manual and computerized approaches.

NUMBER OF SUBJECTS	100 total participants
SUBJECT SELECTION CRITERIA	
Inclusion Criteria:
 
18-70 years of age; meet DSM-V criteria for schizophrenia, schizoaffective disorder or brief psychotic disorder; no medication changes or psychiatric hospitalizations in the past month; SFS raw score of no more than 75.
 
Exclusion Criteria:
 
Active substance use disorder in the past month except mild to moderate cannabis use disorder, schizoaffective, schizopreniform disorder, or brief psychotic disorder; DSM-5 diagnosis other than schizophrenia; Significant neurological/medical disorders; a pacemaker; extensive dental work; claustrophobia; deafness; inability

	to read; current participation in a psychosocial intervention; taking high dose testosterone, estrogen/progesterone. Currently pregnant, breastfeeding, or unwilling to practice birth control during participation.

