### **12.1 Data Sets Analyzed**

All eligible patients who are randomized into the study and receive at least one dose of the study drug (the Safety Population) will be included in the safety analysis.

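### Withdrawn subjects are replaced, no SFS is taken at early withdrawal and no efficacy set or missing-data method is stated, so the SFS comparison may by default omit randomised subjects without a final score

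*Combined protocol and SAP*

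**What the plan says.** **Replacement.** Section 12.4 (Replacement of Subjects) has two sentences: "Subjects who withdraw from the study treatment will be replaced" and "Subjects who withdraw from the study will be replaced". Neither says whether the data of the person replaced stay in the analysis.

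**Early-withdrawal visit.** Section 10.7 has two items: "Record any Adverse Experiences and/or Review subject diary for adverse experiences and exclusionary medication use" and "If given, collect and return unused oxytocin to pharmacy". The SFS is not among them, and Appendix 1 has no early-withdrawal column.

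**Primary analysis.** Section 12.3 (Analysis of Primary Endpoint) specifies "linear regression analyses with SFS change as the primary outcome and drug modeled as a 2-level dummy variable". No missing-data method is given.

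**Analysis sets.** Section 12.1 defines one set, "All eligible patients who are randomized into the study and receive at least one dose of the study drug", and uses it for safety only.

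**Follow-up of those who stop.** Section 11.1 says that subjects who stop study drug "should be encouraged to complete all remaining scheduled visits and procedures". Section 12.3 (Withdrawal of Subjects from the Study) encourages some who leave the study to attend a final visit with the procedures of their next scheduled visit. The limits that decide who this covers are still the template placeholder Visit X.

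**Adaptive allocation.** The synopsis starts response-adaptive randomisation "after the first 60 participants complete the study". Section 8.1 ends enrolment at 55 drug and 40 placebo subjects, counted as assigned.

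**The concern.** A change score needs an end value. A subject who leaves the longitudinal phase without a final SFS cannot enter a regression of SFS change unless the plan says how, and it does not. Someone else is then enrolled in that subject's place, so the final count looks whole.

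The reasons for stopping in section 11.1 include adverse events and non-compliance. Both arise after randomisation and could differ between oxytocin and placebo. If those who leave one arm have systematically worse or better SFS change than those who leave the other, the subjects left for analysis no longer form the randomised comparison. The same selection could enter the interim evaluations that steer allocation.

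The enrolment rule adds a difficulty. If a withdrawn subject still counts as assigned under 8.1, replacement has little meaning. If not, that subject has been taken out of the count. The plan does not say which.

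**Working it through.** The plan gives no dropout rate or missing-data figure to reproduce. The detectable effect size in 12.6 is a separate matter and plays no part here.

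**Inputs from the plan.** 55 drug and 40 placebo subjects (8.1); two-sided alpha 0.05 (12.6).

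**Assumptions.** True effect 0; SFS change with SD 1 in each arm; subjects with poorer change are likelier to leave; both arms refilled to 55 and 40 subjects with a final SFS. The strong link is a correlation ρ = 1/√2 = 0.707 between SFS change and the tendency to stay. If better responders left instead, the sign of the bias would reverse.

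**Shift in one arm.** If a fraction p leaves, the mean change among those who stay is shifted by ρ × φ(z_p) / (1 − p), where z_p is the normal p-quantile and φ the normal density.

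- p = 5%: 0.707 × 0.1031 / 0.95 = 0.077
- p = 10%: 0.707 × 0.1755 / 0.90 = 0.138
- p = 20%: 0.707 × 0.2800 / 0.80 = 0.247
- p = 30%: 0.707 × 0.3477 / 0.70 = 0.351

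**Bias in the comparison** is the drug-arm shift minus the placebo-arm shift. Type I error comes from 20,000 simulated null trials per row, two-sided t-test.

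| Dropout, drug vs placebo | Link to outcome | Bias (SD) | Type I error |
|---|---|---|---|
| 10% vs 10% | none | 0 | 5.0% |
| 20% vs 20% | none | 0 | 5.1% |
| 20% vs 20% | same in both arms | 0 | 4.9% |
| 10% vs 5% | same in both arms | 0.138 − 0.077 = 0.06 | 6.5% |
| 20% vs 10% | same in both arms | 0.247 − 0.138 = 0.11 | 8.9% |
| 30% vs 10% | same in both arms | 0.351 − 0.138 = 0.21 | 21.6% |
| 20% vs 20% | drug arm only | 0.247 − 0 = 0.25 | 24.8% |

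A separate simulation of 6,000 trials per cell, with the link in one arm only, gave 23.8% at 20% dropout and ρ = 0.7. At 15% and ρ = 0.5 it gave a bias of 0.13 SD and about 10%.

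**Rough check of one row.** The standard error is √(1/55 + 1/40) = 0.208. For 20% vs 10%, 0.110 / 0.208 = 0.53, and Φ(−1.43) + Φ(−2.49) = 0.076 + 0.006 = 8.2%. The simulated 8.9% is a little higher because selection narrows the spread among those who stay.

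**Does replacement cause the bias?** The 20% vs 10% case was rerun without replacement. The bias was again 0.11 SD, with type I error 8.2%. Replacement leaves the bias unchanged.

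**How much loss replacement can hide.** Reaching 95 subjects with a final SFS means randomising 95 / (1 − p): 100 at 5%, 106 at 10%, 119 at 20% and 136 at 30%.

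**The case against.** The strongest reply is that the plan does not tell anyone to discard data.

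- **Treatment stoppers.** Section 11.1 asks that they be encouraged to finish all visits, and Appendix 1 places social functioning tests at Visit 5. They can therefore have a final score.
- **Study withdrawals.** Some are to be encouraged to attend a final visit. For a person leaving in the chronic period, the next scheduled visit is Visit 5.
- **The later SAP.** The opening of section 12 promises a detailed SAP, which may modify the analysis.

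These points stand in part, and they rule out several stronger readings.

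- A reader might infer that the comparison becomes completers-only. The plan never uses that term or describes a complete-case analysis; exclusion is what happens by default when it is silent.
- A reader might infer that nobody who leaves can give an SFS. The final-visit provision contradicts that, although it cannot be applied while its limits read Visit X.
- A reader might infer that replacement itself biases the result. The rerun without replacement shows otherwise.
- A reader might infer that the adaptive updates use completers' data only, or that replacements are allocated at the adapted ratio. The synopsis gives completion by 60 subjects as a starting point. It does not say whose data feed the updates, and no section says how replacements are assigned.

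Losses before the longitudinal randomisation would not bias that comparison. Section 4.1 places this randomisation after the fMRI phase, while Appendix 1 marks randomisation at Visit 1, so the boundary is unclear.

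The promised SAP does not close the gap. It is due before the final analysis, whereas the interim evaluations start after 60 subjects have completed. It also cannot recover an SFS that was never collected.

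**Conclusion.** The concern holds as an omission with a possible bias. As written, the SFS comparison may leave out randomised subjects without a final SFS, and replacement would conceal how many there were. Whether this matters depends on dropout after the longitudinal randomisation being related to outcome differently in the two arms.

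The bias is 0 when dropout is unrelated to outcome, or equal with the same link in both arms. It is about 0.06 to 0.11 SD, with type I error 6.5% to 9%, for modest imbalance with a common link. It is about 0.25 SD, with 24% to 25%, for 20% dropout with a strong link in one arm only. Every dropout rate and correlation behind these figures is an assumption, so they show sensitivity and do not forecast this trial; heavier or more uneven dropout would exceed the last row. The change is worth making because it is cheap and the score cannot be recovered later.

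**What to change.** 1. **Collect the score.** Add the SFS to the early-withdrawal visit in 10.7, and fill in the Visit X limits in 12.3 (Withdrawal of Subjects from the Study).
2. **Define the set.** State in 12.1 and in 12.4 (Replacement of Subjects) that the primary efficacy set is everyone randomised to the longitudinal phase, analysed as assigned, and that replaced subjects' data stay in. Allow replacement without retention only before that randomisation, and reconcile 4.1 with Appendix 1 on when it takes place.
3. **State the method.** Analyse all available SFS values (baseline, Visit 4, and Visit 5 or withdrawal) with a likelihood-based repeated-measures model. Include the chronic-period assessment only if it is the SFS, since 10.5 does not name the instrument. Add a sensitivity analysis for missing data. The model assumes missingness is explained by observed values, whereas the scenarios above tie dropout to the subject's own change. The extra SFS and the sensitivity analysis are therefore both needed.
4. **Use one set throughout.** Apply the same set to the adaptive updates, and fix it before the first one.

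The cost is protocol and SAP wording plus one questionnaire at an existing visit. The estimate may be slightly diluted compared with one restricted to subjects who finished treatment.
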